10.3. EXPLORATORY ENDPOINTS

10.3.1. 30 Second Sit to Stand Test

Changes from baseline will be analysed using a MMRM. The model will include fixed terms for treatment, visit and the treatment-by-visit interaction. The model will also include the stratification mutation factor, continuous baseline sit to stand score and continuous baseline distance walked during the 12MWT as covariates. An unstructured covariance structure will be used, and the model will allow the covariance matrix to differ between treatment groups. If the analysis fails to converge, then an ANCOVA will be used, which will analyse the change from baseline at Week 24 and at Week 12 separately. The ANCOVA model will include a fixed term for treatment and the mutation stratification factor, continuous baseline sit to stand score and continuous baseline distance walked during the 12MWT as covariates. The Kenward-Rogers approximation will be used to estimate the denominator degrees of freedom. The treatment comparison for the change from baseline at each visit will be estimated. The estimates, standard errors, 95% confidence intervals and associated p-values will be presented for each visit.

Observed and change from baseline values will be summarized by visit, both including and excluding predicted values, using descriptive statistics. Predicted values for a subject will be the predicted values from the MMRM analysis. The associated 95% confidence intervals for the observed and change from baseline means will also be presented. In addition, the number of subjects with an imputed count of 0 at the visit will be summarized.

Mean plots of observed and change from baseline values, with 95% confidence intervals, will be presented by treatment group with visit on the x-axis. A reference line for no change (i.e., $y=0$) will be included in the change from baseline plot.

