10.1.3. Summaries and Plots

Observed, change from baseline and percent change from baseline values will be summarized by visit, both including and excluding imputed values. The imputed summary statistics will be based on Rubin's methodology (Rubin 1987⁵) to combine the means and standard errors from the imputed data sets. The associated 95% confidence intervals for the observed, change from baseline and percent change from baseline means will also be presented.

Mean plots for observed, change from baseline and percent change from baseline values, with 95% confidence intervals, will be presented by treatment group with visit on the x-axis. A reference line for no change (i.e., $y=0$) will be included in the change from baseline and percent change from baseline plots.

Spaghetti plots for the changes from baseline will be plotted over time. The plots will be split by treatment group. The y-axis will be uniform across the plots to allow comparisons. A reference line for no change (i.e., $y=0$) will be included.

A plot of the proportion of subjects achieving no change or an increase in 12MWD at Week 24 will be presented by treatment group. The x-axis will present the change in 12MWD at Week 24 (starting at 0m to maximum change achieved at Week 24) and the y-axis will present the proportion of subjects who achieve this change as a percentage. A corresponding summary table will present proportion of subjects achieving no change or an increase in 12MWD at Week 24 at incremental cut points of 20m. This plot and table will use the average values for subjects across the imputed datasets (including imputations for intercurrent events).

The number of stops and the number of falls will be summarized by visit. If a subject does not walk for the full 12 minutes, then this will be counted as an additional stop when summarizing.

All data will be listed together with changes from baseline, percent change from baseline and assessments imputed due to being at least possibly related to the subject's PMM will be identified. The pre and post exercise measurement for heart rate, blood pressure and RPP scale score will be listed separately, along with their changes from pre-test.

12MWD values, mean, median, minimum and maximum will all be presented to 2 decimal places and SD will be presented to 3 decimal places.

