Changes from baseline for the 8 scale scores will be analysed using a MMRM. The model will include fixed terms for treatment, visit and the treatment-by-visit interaction. The model will also include the stratification mutation factor, continuous baseline scale score and continuous baseline distance walked during the 12MWT as covariates. An unstructured covariance structure will be used, and the model will allow the covariance matrix to differ between treatment groups. If the analysis fails to converge, then a Toeplitz structure will be used. The Kenward-Rogers approximation will be used to estimate the denominator degrees of freedom. The treatment comparison for the change from baseline at each visit will be estimated. The estimates, standard errors, 95% confidence intervals and associated p-values will be presented for each visit.

Observed and change from baseline values will be summarized at each visit both including and excluding predicted values using descriptive statistics for the 8 scale scores. Predicted values for a subject will be the predicted values from the MMRM analysis. The associated 95% confidence intervals for the observed and change from baseline means will also be presented.

Mean plots of observed and change from baseline values, with 95% confidence intervals, will be presented by treatment group with visit on the x-axis. A reference line for no change (i.e., $y=0$) will be included in the change from baseline plot.

Categorical shift tables of change from baseline for each scale score showing improvement (at least a 4-point increase in score), no change (less than a 4-point change in either direction) or worsening (at least a 4-point decrease in score) at each visit will be summarized. The table will include categories for withdrawn and missing. Percentages will not be presented for the withdrawn and missing rows, and the percentages presented will use the number of non-missing values as the denominator. In addition, to account for subjects at the extreme ends of the scale, the shift table will also include the percent improving or worsening based on those subjects who have the potential to improve or

worsen respectively. Where a 4-point change in score indicates an improvement or worsening, subjects with the potential to improve will have a baseline score of 96 or below; similarly, for those with a potential to worsen they will have a baseline score of 4 or more.

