Scale scores and changes from baseline will be listed separately from the raw data.

Scale score values will be presented to 0 decimal places.

10.3.5. Modified Fatigue Impact Scale (MFIS) – Total, Physical, Cognitive and Psychosocial Sub-scale Scores

Changes from baseline will be analysed using a MMRM for each of the scores. The model will include fixed terms for treatment, visit and the treatment-by-visit interaction. The model will also include the stratification mutation factor, continuous baseline MFIS score and continuous baseline distance walked during the 12MWT as covariates. An unstructured covariance structure will be used, and the model will allow the covariance matrix to differ between treatment groups. If the analysis fails to converge, then a Toeplitz structure will be used. The Kenward-Rogers approximation will be used to estimate the denominator degrees of freedom. The treatment comparison for the change from baseline at each visit will be estimated. The estimates, standard errors, 95% confidence intervals and associated p-values will be presented for each visit.

Observed, change from baseline and percent change from baseline values will be summarized by visit both including and excluding predicted values using descriptive statistics. Predicted values for a subject will be the predicted values from the MMRM analysis. The associated 95% confidence intervals for the observed and change from baseline means will also be presented.

Mean plots of observed, change from baseline and percent change from baseline values, with 95% confidence intervals, will be presented by treatment group with visit on the x-axis. A reference line for no change (i.e., $y=0$) will be included in the change from baseline and percent change from baseline plots.

Spaghetti plots for the changes from baseline will be plotted over time. The plots will be split by treatment group. The y-axis will be uniform across the plots to allow comparisons. A reference line for no change (i.e., $y=0$) will be included.

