10.3.6. Brief Pain Inventory (BPI) Short Form

Changes from baseline for pain severity and pain interference will be analysed using a MMRM. The model will include fixed terms for treatment, visit and the treatment-by-visit interaction. The model will also include the stratification mutation factor, continuous baseline score and continuous baseline distance walked during the 12MWT as covariates. An unstructured covariance structure will be used, and the model will allow the covariance matrix to differ between treatment groups. If the analysis fails to converge, then a Toeplitz structure will be used. The Kenward-Rogers approximation will be used to estimate the denominator degrees of freedom. The treatment comparison for the change from baseline at each visit will be estimated. The estimates, standard errors, 95% confidence intervals and associated p-values will be presented for each visit.

Observed and change from baseline values will be summarized at each visit both including and excluding predicted values using descriptive statistics for the pain severity and pain interference scores. Predicted values for a subject will be the predicted values from the MMRM analysis. The associated 95% confidence intervals for the observed and change from baseline means will also be presented.

Mean plots of observed and change from baseline values, with 95% confidence intervals, will be presented by treatment group with visit on the x-axis. A reference line for no change (i.e., $y=0$) will be included in the change from baseline plot.

Categorical shift tables of change from baseline for pain severity and pain interference showing improvement (at least a 1.5-point decrease in score), no change (less than a 1.5-point change in either direction) or worsening (at least a 1.5-point increase in score) at each visit will be summarized. The table will include categories for withdrawn and missing. Percentages will not be presented for the withdrawn and missing rows, and the percentages presented will use the number of non-missing values as the denominator. In addition, to account for subjects at the extreme ends of the scale, the shift table will also include the percent improving or worsening based on those subjects who have the potential to improve or worsen respectively.

The summary and MMRM analysis may be repeated excluding subjects who have a baseline pain severity score <4.

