Pain severity and pain interference scores and changes from baseline will be listed with the raw data.

10.3.7. Work Productivity and Activity Impairment Questionnaire: Specific Health Problems (WPAI: SHP)

Changes from baseline for WPAI scores, except percent activity impairment, will be analysed using a MMRM for subjects who were employed at baseline. The model will include fixed terms for treatment, visit and the treatment-by-visit interaction. The model will also include the stratification mutation factor, continuous baseline score and continuous baseline distance walked during the 12MWT as covariates. An unstructured covariance structure will be used, and the model will allow the covariance matrix to differ between treatment groups. If the analysis fails to converge, then a Toeplitz structure will be used. The Kenward-Rogers approximation will be used to estimate the denominator degrees of freedom. The treatment comparison for the change from baseline at each visit will be estimated. The estimates, standard errors, 95% confidence intervals and associated p-values will be presented for each visit. The analysis will be repeated for percent of activity impairment which will be based on all subjects.

WPAI scores, except percent activity impairment, will only be summarized for those subjects who are employed. Observed and change from baseline values will be summarized by visit both including and excluding predicted values using descriptive statistics for the 4 WPAI scores. Predicted values for a subject will be the predicted values from the MMRM analysis. The associated 95% confidence intervals for the observed and change from baseline means will also be presented.

Mean plots of observed and change from baseline values, with 95% confidence intervals, will be presented by treatment group with visit on the x-axis. A reference line for no change (i.e., $y=0$) will be included in the change from baseline plot.

WPAI score values will be presented to 0 decimal places.

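### In six exploratory sections of the SAP, by-arm SDs and 95% CIs that include MMRM predictions will be too narrow, because no variance rule accounts for the predictions

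*SAP*

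**What the plan says.** Six sections share one rule. For 30STS (SAP 10.3.1): "Observed and change from baseline values will be summarized by visit, both including and excluding predicted values, using descriptive statistics". SF-36 (10.3.4) is "summarized at each visit both including and excluding predicted values using descriptive statistics for the 8 scale scores", MFIS (10.3.5) is "summarized by visit both including and excluding predicted values using descriptive statistics", BPI (10.3.6) is "summarized at each visit both including and excluding predicted values using descriptive statistics for the pain severity and pain interference scores" and WPAI (10.3.7) is "summarized by visit both including and excluding predicted values using descriptive statistics for the 4 WPAI scores". Step count (10.3.2) has the same pair of summaries. It does not repeat the reference to descriptive statistics, but it sets the display precision for mean, median, minimum, maximum and SD.

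Each section then says where the predictions come from: "Predicted values for a subject will be the predicted values from the MMRM analysis". Each also asks for intervals, in 10.3.1 as "The associated 95% confidence intervals for the observed and change from baseline means will also be presented". SAP 8.2 sets the default for continuous variables: n, mean, SD, median, minimum and maximum.

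For 12MWD (10.1.3) and PROMIS (10.2.1) the SAP handles the same task differently. Summaries with imputed values use Rubin's method "to combine the means and standard errors from the imputed data sets". None of the six exploratory sections has a counterpart to this.

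**The concern.** An MMRM point prediction is an estimated expected value. It lies on the fitted surface and has none of the scatter that a real measurement would have. If predictions are placed among the observed values and summarised in the ordinary way, two things happen: the SD falls, and n rises to the full count although no information has been added beyond what the model borrowed. Both shrink the standard error of the arm mean. The median, minimum and maximum are affected too.

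The clinical study report would then show two by-arm intervals per visit, and the invalid one would look more precise. If the arms differ in missing data, the distortion differs between arms, and a reader could not correct it from the table.

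**Working it through.** **Inputs.** The documents give no SD, CI or missing-data rate for these endpoints, so there is no stated figure to reproduce on this exact point. The only guide to missingness is the sample-size section (SAP 3.5, Protocol 8.2.2). That calculation reproduces: with a 60 m effect, SD 125 m, two-sided 5% and 90% power, the normal formula gives 92 per arm against the stated 93, and power at 93 per arm is 90.5% (90.3% with the t distribution). The increase from 186 to about 200 subjects implies a loss of 1 − 186/200 = 7%.

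**Assumptions.** Let m be the share of values missing completely at random, and R² the share of variance that the prediction explains. R² = 0 corresponds to filling in the arm mean. Higher values correspond to predictions that use covariates or the subject's other visits. The SAP does not say which kind of prediction is meant, so R² is taken from 0 to 0.7.

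**Formulas** (σ is the true SD, n the full number of subjects):

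- SD after filling in = σ·√[(1 − m) + m·R²]
- Naive SE = that SD / √n
- Correct SE = (σ/√n)·√[(1 − R²)/(1 − m) + R²]
- Width ratio = naive SE / correct SE
- Coverage = 2Φ(1.96 × width ratio) − 1

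**Example, m = 0.20 and R² = 0.5.** The SD factor is √(0.80 + 0.10) = 0.949. The correct-SE factor is √(0.5/0.8 + 0.5) = √1.125 = 1.061. The width ratio is 0.949/1.061 = 0.894, and coverage is 92.0%.

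**Results** (SD ratio / width ratio / coverage):

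| m | R² = 0 | R² = 0.5 | R² = 0.7 |
|---|---|---|---|
| 7% | 0.964 / 0.930 / 93.2% | 0.982 / 0.964 / 94.1% | 0.989 / 0.978 / 94.5% |
| 10% | 0.949 / 0.900 / 92.2% | 0.975 / 0.949 / 93.7% | 0.985 / 0.969 / 94.2% |
| 20% | 0.894 / 0.800 / 88.3% | 0.949 / 0.894 / 92.0% | 0.970 / 0.935 / 93.3% |
| 30% | 0.837 / 0.700 / 83.0% | 0.922 / 0.837 / 89.9% | 0.954 / 0.898 / 92.2% |

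**Check by simulation** (100 per arm, 8,000 runs per setting). Missing values were filled with the arm mean, or by regression on an earlier visit with correlation 0.5 or 0.7. Coverage of the filled-in CI was 93.0-94.1% at 7% missing, 88.1-92.4% at 20% and 82.7-89.9% at 30%. The observed-only CI covered 94.8-95.5% throughout.

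**Where missing values are likeliest.** After a subject stops study drug, the minimum efficacy assessments requested at Weeks 12 and 24 are the 12MWT and MFIS (SAP 8.3.1, Protocol 6.9). The other five endpoints in this group can then be missing. An early termination assessment may be assigned to a visit if it falls in the analysis window (SAP 8.4), but step count is not scheduled at that visit.

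**The case against.** The strongest reply is that little depends on these intervals. Every summary is also given without predictions. Treatment differences, SEs, CIs and p-values come from the MMRM itself. The endpoints are exploratory and outside the fixed sequence in SAP 8.2. All of this stands, and it limits the consequence to one of two descriptive versions.

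A second reply is that the SAP never states that predictions are to be treated as observed; this is inferred because no other rule is given. That is true, but the sections name ordinary descriptive statistics (10.3.2 by way of its precision rule), SAP 8.2 supplies the default, and Rubin pooling is written out only for 12MWD and PROMIS. A programmer who followed the text would compute the ordinary SD and CI.

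Four stronger readings are tempting, and the documents do not support them:

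- **The error bars in the mean plots are wrong.** The sections do not say whether the plots use data with or without predictions. This is an ambiguity to settle, not an established error.
- **Step count and WPAI are worst because one is optional and the other covers only employed subjects.** Subjects with no diary data are excluded (SAP 4.5), and only those with a derived step count are analysed (10.3.2). The three work-related WPAI scores are modelled for subjects employed at baseline and summarised only for the employed (10.3.7). Such subjects leave the denominator and are not predicted. Intermittent gaps remain possible.
- **The gap between the two printed intervals measures the error.** Borrowing from a correlated visit brings a real gain in precision, so the observed-only width is the wrong yardstick. At 40% missing and correlation 0.6, a filled-in SE of 0.67 times the observed-only SE looks 33% too narrow. The correct SE is √(1 − 0.36 × 0.4) = 0.925 times the observed-only SE, so the shortfall is 1 − 0.67/0.925, about 28%.
- **The distortion is large.** That needs missingness of 20% or more with weak prediction. The documents give no such rate.

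**Conclusion.** The rule is wrong as written, with minor severity. The by-arm SDs and 95% CIs in the summaries that include predictions will understate uncertainty in all six sections whenever values are missing and prediction is imperfect. At the 7% loss implied by 186/200, the CI is about 2-7% narrower than it should be. At 20% missing it is about 6-20% narrower, with coverage of roughly 88-93%. Both ranges run from R² = 0.7 to R² = 0.

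The size rests on the assumed missing fractions, the assumed R² and values missing completely at random; the direction does not depend on the particular values of m and R². MFIS should be the least exposed of the six, because it is still requested after drug is stopped. No inferential result in the SAP is affected.

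**What to change.** In SAP 10.3.1, 10.3.2 and 10.3.4 to 10.3.7, replace the descriptive SD and CI in the summaries that include predictions with the MMRM least-squares mean, its model SE and 95% CI, per arm and visit. Alternatively, use multiple imputation with Rubin pooling, as in 10.1.3 and 10.2.1. The models are fitted to change from baseline, so summaries of visit values or percent change either stay observed-only or take the multiple-imputation route.

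Add one sentence saying that the mean-plot CIs come from that same source or from observed data only. Keep the observed-only summaries as they are.

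The cost is SAP wording and table-shell edits. With the first option the estimates come from models already planned, and no new data are needed. The intervals become slightly wider.

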10.3.2. Pedometer Step Count

Only subjects who have at least one median and average daily step count derived for a visit will be analysed. Changes from baseline for each endpoint will be analysed using a MMRM. The model will include fixed terms for treatment, visit and the treatment-by-visit interaction. The model will also include the stratification mutation factor, sex, continuous baseline pedometer count, age as a continuous variable and continuous baseline distance walked during the 12MWT as covariates. An unstructured covariance structure will be

used, and the model will allow the covariance matrix to differ between treatment groups. If the analysis fails to converge, then a Toeplitz structure will be used. The Kenward-Rogers approximation will be used to estimate the denominator degrees of freedom. The treatment comparison for the change from baseline at each visit will be estimated. The estimates, standard errors, 95% confidence intervals and associated p-values will be presented for each visit.

Observed, change from baseline and percent change from baseline values will be summarized by visit, both including and excluding predicted values. Predicted values for a subject will be the predicted values from the MMRM analysis. The associated 95% confidence intervals for the observed, change from baseline and percent change from baseline means will also be presented. In addition, the number of subjects with a daily step count <500 or $\geq 20,000$ at the visit will be summarized.

Mean plots of observed value, change from baseline and percent change from baseline values, with 95% confidence intervals, will be presented by treatment group with visit on the x-axis. A reference line for no change (i.e., $y=0$) will be included in the change from baseline and percent change from baseline plots.

Spaghetti plots of the individual median and average daily step count change from baseline and percent change from baseline will be plotted over time. The plots will be split by treatment group. The y-axis will be uniform across the plots to allow comparisons. A reference line for no change (i.e., $y=0$) will be included.

Median and average daily step count values mean, median, minimum and maximum will all be presented to 0 decimal places and SD will be presented to 1 decimal places.

10.3.3. Patient Global Impression of Severity (PGIS) Score - Muscle Symptoms and Fatigue Symptoms

Missing values will be imputed using the technique of multiple imputations. Ordinal regression will be used to impute the monotone missing data. Week 12 and Week 24 data will then be analysed separately using ordinal logistic regression analysis for each symptom. The model will include a fixed term for treatment. The model will also include the stratification mutation factor, baseline score and baseline distance walked during the 12MWT as covariates. If there are few counts in one or more of the response categories causing issues with model convergence then categories will be combined in a logical way (e.g., only adjacent categories will be combined) to reduce the number of categories. The proportional odds assumption will be checked using the Score test; if the assumption does not hold then a partial or non-proportional model will be considered. The estimated odds ratios, p-values and 2-sided 95% confidence intervals for the odds ratios will be presented.

Categorical shift tables from baseline at each visit will be summarized including marginal totals. The table will include categories for withdrawn and missing. Percentages will not be presented for the withdrawn and missing rows, and the percentages presented will use the number of non-missing values as the denominator. In addition, to account for subjects at the extreme ends of the scale, the shift table will be repeated for improvement, no change or worsening from baseline at each visit, based on those subjects who have the potential to improve or worsen, respectively.

Stacked bar charts will be presented for the proportion of subjects at each of the PGIS scores by visit for each of the treatment groups. The categories will include each of the PGIS levels and missing and withdrawn.

10.3.4. 36 Item Short Form Survey (SF-36)

Changes from baseline for the 8 scale scores will be analysed using a MMRM. The model will include fixed terms for treatment, visit and the treatment-by-visit interaction. The model will also include the stratification mutation factor, continuous baseline scale score and continuous baseline distance walked during the 12MWT as covariates. An unstructured covariance structure will be used, and the model will allow the covariance matrix to differ between treatment groups. If the analysis fails to converge, then a Toeplitz structure will be used. The Kenward-Rogers approximation will be used to estimate the denominator degrees of freedom. The treatment comparison for the change from baseline at each visit will be estimated. The estimates, standard errors, 95% confidence intervals and associated p-values will be presented for each visit.

Observed and change from baseline values will be summarized at each visit both including and excluding predicted values using descriptive statistics for the 8 scale scores. Predicted values for a subject will be the predicted values from the MMRM analysis. The associated 95% confidence intervals for the observed and change from baseline means will also be presented.

Mean plots of observed and change from baseline values, with 95% confidence intervals, will be presented by treatment group with visit on the x-axis. A reference line for no change (i.e., $y=0$) will be included in the change from baseline plot.

Categorical shift tables of change from baseline for each scale score showing improvement (at least a 4-point increase in score), no change (less than a 4-point change in either direction) or worsening (at least a 4-point decrease in score) at each visit will be summarized. The table will include categories for withdrawn and missing. Percentages will not be presented for the withdrawn and missing rows, and the percentages presented will use the number of non-missing values as the denominator. In addition, to account for subjects at the extreme ends of the scale, the shift table will also include the percent improving or worsening based on those subjects who have the potential to improve or

worsen respectively. Where a 4-point change in score indicates an improvement or worsening, subjects with the potential to improve will have a baseline score of 96 or below; similarly, for those with a potential to worsen they will have a baseline score of 4 or more.

Scale scores and changes from baseline will be listed separately from the raw data.

Scale score values will be presented to 0 decimal places.

10.3.5. Modified Fatigue Impact Scale (MFIS) – Total, Physical, Cognitive and Psychosocial Sub-scale Scores

Changes from baseline will be analysed using a MMRM for each of the scores. The model will include fixed terms for treatment, visit and the treatment-by-visit interaction. The model will also include the stratification mutation factor, continuous baseline MFIS score and continuous baseline distance walked during the 12MWT as covariates. An unstructured covariance structure will be used, and the model will allow the covariance matrix to differ between treatment groups. If the analysis fails to converge, then a Toeplitz structure will be used. The Kenward-Rogers approximation will be used to estimate the denominator degrees of freedom. The treatment comparison for the change from baseline at each visit will be estimated. The estimates, standard errors, 95% confidence intervals and associated p-values will be presented for each visit.

Observed, change from baseline and percent change from baseline values will be summarized by visit both including and excluding predicted values using descriptive statistics. Predicted values for a subject will be the predicted values from the MMRM analysis. The associated 95% confidence intervals for the observed and change from baseline means will also be presented.

Mean plots of observed, change from baseline and percent change from baseline values, with 95% confidence intervals, will be presented by treatment group with visit on the x-axis. A reference line for no change (i.e., $y=0$) will be included in the change from baseline and percent change from baseline plots.

Spaghetti plots for the changes from baseline will be plotted over time. The plots will be split by treatment group. The y-axis will be uniform across the plots to allow comparisons. A reference line for no change (i.e., $y=0$) will be included.

Categorical shift tables of change from baseline showing improvement (at least a 4-point decrease in score), no change (less than a 4-point change in either direction) or worsening (at least a 4-point increase in score) at each visit will be summarized. The table will include categories for withdrawn and missing. Percentages will not be presented for the withdrawn and missing rows, and the percentages presented will use the number of non-missing values as the denominator. In addition, to account for subjects at the extreme ends

of the scale, the shift table will also include the percent improving or worsening based on those subjects who have the potential to improve or worsen respectively.

As a sensitivity analysis the main analysis will be repeated excluding subjects from the Netherlands site to assess if there was an impact due to the incorrect recall period being included on the questionnaire for subjects at this site.

Total and sub-scale scores and changes from baseline will be listed separately from the raw data.

